8.5.3. Anthropometric profile

Descriptive summaries will be provided for the following parameters to evaluate the metabolic profile of subjects:

- Weight, Height and BMI
- Waist circumference
- Hip circumference
- CCI
- CCI
- Tanita scale parameters (total body fat percent, total body water percent, muscle mass, and bone mineral mass)

Subjects with cosmetic procedures of the torso/thighs (exclude face/neck) including but not limited to liposuction/liposculpture/implants will be excluded from the above summary statistics at Month 12 (OLI and BIK)/Month 11 (D2I).

Data collected after initiation of lipid-modifying agents on treatment will be considered non-evaluable for anthropometric profile summaries (while on-treatment strategy).

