16.7.2.2. Handling of Missing data for Statistical Analysis

Element	Reporting Detail
Snapshot	
 • In the Snapshot dataset, participants without HIV-1 RNA data in the assessment window for the visit of interest (due to missing data or discontinuation of IP prior to the visit window) do not belong to 'HIV-1 RNA < 50 c/mL (or <200 c/mL)'. The nature of this missing data will be further classified in Snapshot summaries as either 'HIV-1 RNA≥50' or 'No Virologic Data at Week X'. See Appendix 9: Snapshot Algorithm Details.
Lipid Evaluable	
 • For subjects with lipid-modifying agent use, lipid assessments will be considered non-evaluable (equal to missing) after initiation without any imputation. • If participants take lipid modifying agents within 12 weeks prior to the start of the study treatment, all the post-baseline values will be non-evaluable. • The lipid evaluability rules will be used for the following displays: 
 Summary of Fasting TC/HDL ratio Change from Baseline Summary of Fasting Lipids Percentage Changes from Baseline Summary of Chemistry Changes from Baseline • All other displays of lipids (i.e. toxicity tables and NCEP tables) will use observed fasting data, without considering lipid evaluability. • The same rule of "lipid evaluable" will be applied to anthropometric parameters as specified in Section 8.5.3: 
 - Weight, Height and BMI - Waist circumferences - Hip circumference - CCI [REDACTED] - CCI [REDACTED] - Tanita scale parameters (total body fat percent, total body water percent, muscle mass, and bone mineral mass).

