3.60.	Safety	VS1	Summary of Anthropometric Parameters by Visit (Lipid Evaluable)	Q2M and BIK only. Include all planned visits Include: weight, height, BMI, waist and hip circumference, CCI and Tanita scale measurements (total body Fat %, bone mass, muscle mass, TBW%)	M6
3.61.	Safety	VS1	Summary of Anthropometric Parameters by Visit Excluding Subjects with Cosmetic procedures (Lipid Evaluable)	Q2M and BIK only add footnote: Cosmetic procedures include procedures of the torso/thighs (exclude face/neck) including but not limited to liposuction/liposculpture/implants.	M12
3.62.	Safety	VS1	Summary of Change from Baseline in Anthropometric Parameters by Visit (Lipid Evaluable)	Q2M and BIK only Same parameters as 3.60	M6

Safety: Tables					
No.	Population	GSK Standard/ Example Shell	Title	Programming Notes	Deliverable [Priority]
3.63.	Safety	VS1	Summary of Change from Baseline in Anthropometric Parameters by Visit Excluding Subjects with Cosmetic Procedures (Lipid Evaluable)	
Q2M and BIK only
 
add footnote:
 
Cosmetic procedures include procedures of the torso/thighs (exclude face/neck) including but not limited to liposuction/liposculpture/implants.
	M12

Safety: Tables					
No.	Population	GSK Standard/ Example Shell	Title	Programming Notes	Deliverable [Priority]
Metabolic Syndrome					
3.64.	Safety	SAF_T15	Summary of Percent of Subjects with Metabolic Syndrome and Risk Factors (Maintenance Phase)	
Q2M and BIK only
 
In addition to Metabolic syndrome, also include percentage for each of the 5 factors:
 
Elevated waist circumference; Elevated triglycerides; Reduced HDL-C; Elevated blood pressure; Elevated fasting glucose
	M6, M12
3.65.	Safety	SAF_T12	Summary of Shift in Metabolic Syndrome and Risk Factors at M12 (OLI and BIK) /M11(D2I) from Baseline	
Update to M5/6 for M6 RE. Q2M and BIK only.
 
Shift table from baseline to M5/6 or M11/12, Yes/No/Missing
	M6, M12
3.66.	Safety	SAF_T10	Statistical Analysis of Proportion of Subjects with Metabolic Syndrome at M12 (OLI and BIK) /M11(D2I) – Logistic Regression		M6, M12

Safety: Tables					
No.	Population	GSK Standard/ Example Shell	Title	Programming Notes	Deliverable [Priority]
Cardiovascular Risk and Substance Use					
3.67.	Safety	207966/primary_15/T1.22	Summary of Cardiovascular Risk Assessments by Visit (Maintenance Phase)	Add section header for each visit. For month 6, only calculate Framingham equation For month 12, also include smoking status Q2M vs. BIK	M6, M12

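### The lipid-evaluability filter is extended to body measurements, leaving waist, hip and body composition with no unrestricted change-from-baseline summary

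*SAP*

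**What the plan says.** Section 8.5.3 plans descriptive summaries of weight, height, BMI, waist, hip and Tanita scale parameters to describe the metabolic profile. Two further items in its list are redacted and are not considered here. The section then sets the restriction: "Data collected after initiation of lipid-modifying agents on treatment will be considered non-evaluable for anthropometric profile summaries". It calls this a while on-treatment strategy.

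Section 16.7.2.2 sets out the rule for lipids first. After a lipid-modifying agent is started, "lipid assessments will be considered non-evaluable (equal to missing) after initiation without any imputation". A second clause covers earlier use: "If participants take lipid modifying agents within 12 weeks prior to the start of the study treatment, all the post-baseline values will be non-evaluable". Three lipid and chemistry displays follow the rule; lipid toxicity and NCEP tables are exempt and use observed fasting data. The section then says that the same rule "will be applied to anthropometric parameters as specified in Section 8.5.3", and lists the body measurements by name. No exemption is written for them.

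In the display list (Section 16.15.7), Tables 3.60 to 3.63 carry the Lipid Evaluable label. Tables 3.60 and 3.62 are Month 6 deliverables; 3.61 and 3.63 are for Month 12 and also exclude participants with cosmetic procedures. Tables 3.57, 3.58, 3.59 and 3.81, on weight and/or BMI, lack the label. So do Tables 3.64 and 3.65 on metabolic syndrome and its risk factors, which include waist.

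**The concern.** The SAP gives no reason why a lipid-modifying agent should make a scale or tape measurement unusable. The rule looks like a carry-over from the lipid section, and no other class of medicine triggers it in Section 8.5.3.

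Starting a lipid agent happens after randomisation and is plausibly linked to metabolic change, which is what these tables are meant to describe. Dropping values from that point can remove participants because of how they are doing, and in an open-label trial the starting rate could differ by arm. The pre-study clause removes a further group for the whole of follow-up.

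The while on-treatment label does not fit well either. These participants stay on study treatment. Where the SAP uses that strategy for pregnancy (Section 5.5.1 and Appendix 13), it points to an asymmetry: Q2M participants may continue and BIK participants are withdrawn. No comparable asymmetry is stated here.

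At stake is whether the Month 12 waist, hip and body composition summaries describe the treated population or only those who do not use lipid agents.

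**Working it through.** The SAP attaches no figure to this rule, so there is nothing to reproduce. The check compares the passages and then sizes the loss under stated assumptions.

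**1. Where the filter applies.**

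| Measurement | Displays with the label | Displays without the label |
|---|---|---|
| Waist | 3.60–3.63 | 3.64, 3.65 (only as a metabolic syndrome factor) |
| Hip, Tanita parameters | 3.60–3.63 | no summary; Listing 54 only |
| Weight, BMI | 3.60–3.63 | 3.57 (BMI), 3.58, 3.59 (weight), 3.81 |

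Waist, hip and body composition therefore have no change-from-baseline summary outside the filter. A waist value can count towards metabolic syndrome in Tables 3.64 and 3.65 and still be missing from 3.61 and 3.63. The metabolic syndrome model in Section 8.5.2 uses observed cases. Listing 54 shows all values, so the data are left out of the summaries, not lost.

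**2. Do the passages agree?** Section 8.5.3 names only initiation on treatment. Section 16.7.2.2 also removes earlier users ("all the post-baseline values will be non-evaluable") and says this same rule covers the body measurements, while pointing back to a section that lacks the clause. Section 16.7.2.2 also names weight and BMI without exemption, yet four displays of them are unlabelled. A programmer could read either point two ways.

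**3. Size of the loss (illustration).** Inputs: about 654 participants randomised 2:1 (Section 2.3), so 654 × 2/3 = 436 on Q2M and 654 × 1/3 = 218 on BIK. The total share removed, f, is not in the SAP and is assumed to be 5% to 30%. Number removed = 654 × f; remaining per arm = n × (1 − f); standard error factor = 1/√(1 − f).

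| f | Removed | Remaining Q2M / BIK | SE factor |
|---|---|---|---|
| 5% | 33 | 414 / 207 | 1.03 |
| 10% | 65 | 392 / 196 | 1.05 |
| 20% | 131 | 349 / 174 | 1.12 |
| 30% | 196 | 305 / 153 | 1.20 |

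The last column expresses precision of a mean only; no interval is planned for these parameters.

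**4. Effect on the arm difference (illustration).** If the removed participants' mean change exceeds that of the others by D in both arms, the filtered Q2M − BIK difference departs from the all-participant difference by (f_BIK − f_Q2M) × D. With equal shares this is 0. With assumed shares of 10% on Q2M and 20% on BIK and D = 2 kg, it is (0.20 − 0.10) × 2 = 0.2 kg.

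**The case against.** The strongest reply is that little of consequence depends on the filter.

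- A reader might infer that the plan discards all post-baseline body data of lipid-agent users. It does not. Weight and BMI appear in four unlabelled displays, and Listing 54 is complete. This stands.
- A reader might infer that the weight-gain AESI or the BMI stratification is compromised. Neither is. The AESI is identified from MedDRA terms (Section 16.11.14), with all observed adverse event data kept (Section 8). Stratification uses baseline BMI, which the filter does not touch. This stands.
- A reader might infer that planned confidence intervals widen. Section 8.5.3 plans descriptive summaries, and the overview table in Section 8.1 marks no statistical analysis for these parameters. This stands.
- The pre-study clause is found only in Section 16.7.2.2. If Section 8.5.3 governs, only on-study starters are removed and the loss is probably towards the low end of the range. This stands as an uncertainty, and it shows that the two sections need aligning.
- The rule is prespecified and labelled, and Table 1.22 will report lipid-agent use. That makes the loss visible but does not supply the missing unrestricted summary. Table 1.22 is also on mITT-E, while the anthropometric tables use the Safety population.

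What the reply does not answer is that waist, hip and body composition change is summarised only after the filter, and that no reason is given for it.

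**Conclusion.** The point holds in a limited form. For waist, hip and Tanita body composition, the Month 12 summaries describe a subset selected partly on a post-randomisation event, with no unrestricted version beside them. The SAP's two statements of the rule and its display list also leave the reach of the filter unclear, for pre-study users and for weight and BMI.

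The size cannot be fixed from the document. The loss of about 33 to 196 participants rests on the assumed 5% to 30% share and on the planned 654. A narrower loss figure would need usage rates that the SAP does not give.

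It is tempting to conclude that the arm comparison is biased. The document does not establish that: with equal removed shares and the same D in both arms the difference does not move, and any difference in shares is conjecture. Even then, each arm's mean would still describe only the participants left after the filter. The primary endpoint and the metabolic syndrome analysis are not affected. This is a worthwhile, low-cost correction to descriptive safety tables.

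**What to change.** 1. Produce Tables 3.61 and 3.63 on all observed measurements, keeping the cosmetic-procedure exclusion.
2. Retain the current lipid-evaluable versions as sensitivity tables, labelled as such.
3. Align Section 8.5.3 with Section 16.7.2.2: state whether the sensitivity version removes only values after an on-study start, or also all post-baseline values of users in the 12 weeks before treatment.
4. State that Tables 3.57 to 3.59, 3.64, 3.65 and 3.81 are not filtered, or label them if they are.

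Tables 3.60 and 3.62 belong to the Month 6 analysis and need no rerun for this purpose.

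The cost is two extra displays and a few lines of SAP text. The measurements are already in the visit schedule, so no new data are needed.

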8.5.4. HOMA-Insulin Resistance

HOMA-Insulin Resistance analysis will only be performed when all expected data through Month 12 (OLI and BIK)/Month 11 (D2I) has been received from the laboratory. Statistical estimates for each planned visit will be provided in the Month 12 primary analysis using the MMRM model as describe in the below sections unless otherwise noted. The details of the planned displays are in [Appendix 15: List of Data Displays](#).

Statistical Analyses
Endpoints

 Change from baseline in HOMA-IR at Month 6 (OLI and BIK)/Month 5 (D2I) and at Month 12 (OLI and BIK)/Month 11 (D2I) 
Note: the following subjects will be excluded from the statistical analysis:
 
 diabetic or have taken an anti-diabetic medication up to screening fasting glucose >126mg/dl and HbA1C >6.5% at Day 1 have had a cosmetic procedure including liposuction/liposculpture of the thighs, buttocks, hips and/or abdomen
Covariates

Statistical Analyses

 • Baseline Value (continuous) • Gender at Birth (male, female) • Baseline BMI(<30 kg/m², >=30 kg/m²) • Age (Continuous) • Race (White, Black/African American, Other) • Smoking Status (Never, Current, Former) • Hypertension (Yes vs no) 
Note: Hypertension is defined as having a medical history of hypertension or use of medication treating hypertension (current and past)

Data Handling

 • OC (Observed Case) dataset will be used.
Model Specification

 • Same as in Section 8.4.1
Model Checking & Diagnostics

 • Same as in Section 8.4.1
Model Results Presentation

 • Same as in Section 8.4.1
Sensitivity Analyses

 • Logistic regression models will be performed on the proportion of subjects with HOMA-IR >=2, >=3 or >=4 at Month 12(OLI and BIK)/11(D2I) adjusting for the same covariates as specified in the MMRM analysis (without visit or interaction terms and without log transformation for the baseline value). Odds ratios, confidence intervals and p-values will be presented for all covariates specified in the model. • Upon delivery of data, an assessment regarding the amount of missing data will be made. If the amount of missing HOMA-IR outcome data considered as a result of other impacts such as COVID-19 is substantial, the logistic regression analysis may not be performed. • If the percent of subjects above any of the cutoffs are below 5% of the total number of subjects (observed data), or if complete or quasi-complete separation is observed in the data, then the analysis may not be performed.
Subgroup Analyses

 • Not applicable

9. POPULATION PHARMACOKINETIC (POPPK) ANALYSES

Not applicable.

10. PHARMACOKINETIC ANALYSES

PK data collected for pregnant participants and at withdrawal visits for all subjects will be listed given data availability. Other PK samples are put to storage and there is no planned PK analysis at the time of the interim or the primary analysis. Future amendment will be made if pharmacokinetic data are to be explored further in the future.

11. PHARMACODYNAMIC (AND / OR BIOMARKER) ANALYSES

Not applicable.

12. PHARMACOKINETIC / PHARMACODYNAMIC ANALYSES

There is no plan for PK/PD analysis for the interim or the Month 12 primary analysis. Analysis details will be provided in future amendments if necessary.

13. HEALTH OUTCOMES ANALYSIS

13.1. Endpoint/Variables

- Absolute values and Change from baseline in total “treatment satisfaction” score, and individual item scores of the HIV Treatment Satisfaction Status Questionnaire (HIVTSQs) at Month 12 (OLI and BIK)/Month 11 (D2I), and at Month 6(OLI and BIK)/Month 5(D2I).
- Change in treatment satisfaction using the HIV Treatment Satisfaction Change (HIVTSQc) questionnaire at Month 12 (OLI and BIK)/Month 11 (D2I)(or withdrawal).
- Preference for CAB LA + RPV LA every 2 months compared to an oral BIK single tablet regimen as well as reasons for preference at Month 12 (OLI)/Month 11 (D2I).
- Change from Month 2(OLI)/Month 1(D2I) in Dimension scores (e.g., “Bother of ISRs”, “Leg movement”, “Sleep”, and “Acceptance of ISRs”) and in individual item

scores assessing pain during injection, anxiety before and after injection, willingness to be injected in the future and overall satisfaction with mode of administration over time using the Perception of injection questionnaire (PIN) at Month 12 (OLI and BIK)/Month 11 (D2I), and at Month 6(OLI and BIK)/Month 5(D2I).

CCI

13.2. Summary Measure

Mean treatment difference (Q2M – BIK) in change from day 1 (baseline) at visits of interest for HIVTSQs and HIVTSQc.

Mean change at visits of interest for Change from Month 2(OLI)/Month 1 (D2I) in PIN Dimension and individual item scores.

13.3. Population of Interest

The primary health outcomes analyses will be based on the Intent-to-Treat Exposed population, unless otherwise specified. CCI

CCI Note in the Month 12 analysis, mITT-E will be used in summary tables.

13.4. Strategy for Intercurrent (Post-Randomization) Events

If a participant discontinues treatment prior to the timepoint of interest such that there is no evaluable on-treatment assessment for the timepoint of interest, the data will not be computed or imputed. Assessment window slotting may be implemented for unscheduled and withdrawal visits per Section 16.3.4.

13.5. Statistical Analyses / Methods

Endpoints	Absolute								Change from Maintenance Baseline						
	Stats Analysis			Summary		Individual			Stats Analysis			Summary		Individual	
	T	F	L	T	F	F	L	T	F	L	T	F	F	L	
Treatment Satisfaction Score (HIVTSQs) at Day 1, Month 6(OLI and BIK)/Month 5(D2I), Month 12 (OLI and BIK)/Month 11 (D2I)															
Individual Item Scores by visit				Y				Y ^[3]			Y				
Total Treatment Satisfaction Score				Y				Y			Y				
Treatment Satisfaction Score Change (HIVTSQc) at Day 1, Month 12 (OLI and BIK)/Month 11(D2I)															
Individual Item Scores				Y											
Treatment Satisfaction Score Change	Y			Y											
Treatment Preference for CAB LA + RPV LA every 2 months compared to an oral BIK single tablet regimen as well as reasons for preference															
Treatment: Every 2 Months vs Daily Oral BIK				Y											
Reasons for Preference				Y											
Perception of Injection (PIN) at Month 2(OLI and BIK)/Month 1(D2I), Month 6(OLI and BIK)/Month 5(D2I), Month 12 (OLI and BIK)/Month 11 (D2I) – Q2M only															
Individual Item Scores (Anxiety Before, Pain, Satisfaction, Anxiety After, Willingness)				Y							Y ^[2]				
Dimension scores (e.g., "Bother of ISRs", "Leg movement", "Sleep", and "Acceptance of ISRs")	Y ^[1]			Y							Y ^[2]				
Individual Questionnaire Scores (21 items)				Y											

Endpoints	Absolute								Change from Maintenance Baseline							
	Stats Analysis			Summary			Individual		Stats Analysis			Summary			Individual	
	T	F	L	T	F	F	L	T	F	L	T	F	F	L		
CCI																

NOTES:

Table 1 T = Table, F = Figure, L = Listings, Y = Display generated.

Table 2 Stats Analysis = Represents TFL related to any formal statistical analyses (i.e. modelling) conducted.

Table 3 Summary = Represents TFL related to any summaries (i.e. descriptive statistics) of the observed raw data.

Table 4 Individual = Represents FL related to any displays of individual participant observed raw data.

1. Statistical analysis (i.e. p-value) produced only for the acceptance score comparing to Month 2(OLI)/Month 1(D2I).
2. Change versus Month 2(OLI)/Month 1(D2I) for PIN.
3. Individual items 5 (convenient), 6 (flexible) and 10 (continue).

13.5.1. Statistical Methodology Specification

Details of the planned displays are provided in [Appendix 15: List of Data Displays and](#) will be based on GSK Data Standards and statistical principles.

Unless otherwise specified, endpoints/variables defined in Section 13.1 will be summarised using descriptive statistics and graphically presented (where appropriate). Observed data will be used for summaries and statistical analysis unless otherwise noted.

13.5.1.1. HIVTSQs

Statistical Analyses
HIVTSQS
Endpoints
Change from Maintenance Baseline (Day 1) at Month 6(OLI and BIK)/Month 5(D2I) and at Month 12 (OLI and BIK)/Month 11 (D2I) in:

 • HIVTSQs total treatment satisfaction score • Individual HIVTSQs items 5 (convenience), 6 (flexible), 10 (continue)
Covariates
Baseline score(continuous) Gender at Birth (male, female)

Statistical Analyses
Baseline BMI(<30 kg/m ² , >=30 kg/m ²) Age (<50, >=50 Years) Race (white, non-white)
Model Specification

 • Month 6(OLI and BIK)/Month 5(D2I) Analysis: ANCOVA (analysis of covariance) model will be used for Maintenance Phase data including treatment group plus above covariates. • Month 12 (OLI and BIK)/Month 11 (D2I) Analysis: MMRM (Mixed Model Repeated Measures) will be used including treatment group plus above covariates. No assumptions will be made about the correlations between subject readings (i.e. the correlation matrix for within-subject errors is unstructured): • MMRM (Mix Model Repeated Measures) model with the observed margins (OM) option within PROC MIXED in SAS will be used including treatment group plus the above covariates, with visit as the repeated factor. • The Kenward and Roger method for approximating the denominator degrees of freedom and correcting for bias in the estimated variance-covariance of the fixed effects will be used. • No assumptions about the correlations between a subject's value will be made (the correlation matrix for within-subject errors will be unstructured). This will be estimated by treatment group by specifying "type=UN" and "group=treatment" options in the SAS MMRM models. • In the event that this model fails to converge, alternative correlation structures may be considered such as CSH or CS. Akaike's Information Criteria (AIC) will be used to assist with the selection of covariance structure if needed. • The repeated measures analysis will assume that the treatment difference can vary between visits (i.e. a treatment*visit interaction will be included in the model) . Estimates and 95% confidence intervals will be produced for each visit.
Dataset

 • OC (Observed Case) dataset (with data slotting for the withdrawal/unscheduled visits) will be used. see Section 16.3.4 for details. No additional imputations will be used.
Model Results Presentation

 • Adjusted means for each treatment group with 95% CI • Adjusted treatment difference (Q2M-BIK), 95% CI and the associated p-value for difference • Interaction between treatment and the baseline score

13.5.1.2. HIVTSQc

Statistical Analyses
HIVTSQc
Endpoint

 Treatment Satisfaction Score (Change) at Month 12 (OLI and BIK)/Month 11 (D2I)
Covariates
Gender at Birth (male, female) Baseline BMI(<30 kg/m ² , ≥30 kg/m ²) Age (<50, ≥50 Years) Race (white, non-white)
Model Specification

 An analysis of variance (ANOVA) model will be used with above covariates Adjusted point estimates will be derived as LSMEANS using the observed margins (OM) option within PROC MIXED in SAS. Interactions between treatment and each of the covariates will not be assessed unless CCI [REDACTED] the primary endpoint highlights significant interactions. In this situation, the interaction(s) of interest may be assessed and, if necessary, results will be reported in the clinical study report. If interactions are found to be significant (p<0.10), results may be presented separately by subgroup.
Dataset

 OC (Observed Case) dataset (with data slotting for the withdrawal/unscheduled visits) will be used. see Section 16.3.4 for details. No additional imputations will be used.
Model Results Presentation

 Adjusted means for each treatment group with 95% CI Adjusted treatment difference (Q2M-BIK), 95% CI and the associated p-value for difference

